## 7.1 Hypothesis

The observed rates of increased IOP seen in the absence of planned training in primary eyes in PMA Study CP19-01 were 15.3% (50/327) for IOP  $\geq$  30 mmHg and 7.0% (23/327) for IOP  $\geq$  40 mmHg. Based on Study CP19-01 data from investigators who followed the instructions in the proposed EVO Physician Certification Program regarding removal of OVD (Table 6), it is assumed that the proportion of primary eyes that will reach or exceed an IOP of 30 mmHg is 6% and the proportion of primary eyes that will reach or exceed an IOP of 40 mmHg is 1%.

Site #	Reported Irrigation Volume	with el IOP in s	ry Eyes levated specified ge (n)	Primary Eyes implanted	elevated specifie	es with I IOP in d range n)	All Implanted Eyes
	сс	>/= 30	>/= 40	Ν	>/= 30	>/= 40	Ν
09	10-20 cc	5	0	39	9	0	74
13	20-30 cc	3	0	19	7	0	37
07	10-20 cc	1	0	10	1	0	20
02	> 30 cc	1	0	11	2	0	20
10	10-20 cc	0	0	29	0	0	36
11	20-30 cc	1	0	76	1	0	148
04	> 30 cc	0	0	12	0	0	22
06	10-20 cc	0	0	8	0	0	12
03	10-20 cc	4	0	31	11	0	60
05	20-30 cc	0	0	5	0	0	9
	Total	15	0	240	31	0	438
Proportion, n/N		6.25%	0.00%		7.08%	0.00%	

Table 4: Incidence of elevated IOP in primary eyes for investigators who followed
proposed EVO Physician Certification Program instructions for removal of OVD. 

## 7.2 Study Endpoints and Statistical Analysis

Primary endpoints of this study are:

- the proportion of primary eyes that have IOP ≥ 30 mmHg at 1 6 hours postoperatively
- the proportion of primary eyes that have  $IOP \ge 40 \text{ mmHg at } 1 6 \text{ hours}$  postoperatively

Secondary endpoints of this study are:

- the proportion of fellow eyes that have IOP ≥ 30 mmHg at 1 6 hours postoperatively
- the proportion of fellow eyes that have IOP ≥ 40 mmHg at 1 6 hours postoperatively

The following other endpoints of this study will be analyzed for the entire postoperative follow-up period (including the 1 - 6 hr postop Visit through Visit 4, postop Day 10 - 18):

- Rates of increased IOP in primary and all (primary + fellow) eyes attributed to retained OVD
- Rates of increased IOP in primary and all eyes attributed to other causes (e.g., pupillary block, steroid response, etc.)
- Rates of all categories of AEs (in primary and in all eyes)

The following will also be assessed in this study through postoperative Visit 4 using descriptive statistics:

- Device deficiencies,
- Distribution of lens vault measured by OCT,
- Slit lamp findings and distributions of gradings (e.g., anterior chamber cell and flare)
- Notable ophthalmoscopy findings;
- UDVA and CDVA
- Instances of loss of ≥10 letters of CDVA from baseline, along with analyses of the causes.

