## 5.1.3.1 Postoperative Visit 1 - Operative Day (1 - 6 hours after surgery)

At approximately 1 - 6 hours after surgery, an IOP reading and slit lamp examination in the implanted eye(s) will be conducted. Any complications, AEs, or associated treatment given will be appropriately documented and reported in the CRFs.

## 5.1.4 Postoperative Visits Day 1 – 18

An IOP reading will be performed at these visits in addition to other standard postoperative assessments as part of the normal postoperative standard of care. Any AEs of increased IOP compared to baseline will be documented. Evaluation of the anterior chamber angle is to be performed by gonioscopy or AS-OCT in cases where gonioscopy is contraindicated as presented in Appendix B. Associated treatments will be appropriately documented and reported in the CRFs.

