## 5.1.5 Unscheduled Visits

Additional visits may be scheduled, as necessary, to ensure the safety and well-being of subjects. All additional exams should be fully documented in the source documents and on Unscheduled Visit CRFs, as appropriate. Visits intended to fulfill scheduled visit requirements that fall outside the designated scheduled visit range, are not Unscheduled Visits. In these cases, the visit data will be collected and transcribed to the appropriate scheduled visit CRF.

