## 7.0 STATISTICAL METHODS

Analysis of the superiority of the proportion of primary eyes that have IOP  $\ge$  30 mmHg and IOP  $\ge$  40 mmHg at 1 – 6 hours postoperatively compared with the outcomes of Study CP19-01, i.e., 15.3% (50/327) primary eyes with IOP  $\ge$  30 mmHg, and 7.0% (23/327) primary eyes with IOP  $\ge$  40 mmHg (**Table 3**, below). Analysis of fellow eye rates will be used to support the findings of the two primary eye analyses.

Any deviations from the analysis plan will be documented in the final report.

Adverse Event - Elevated IOP	Primary Eyes (N=327)	All Treated Eyes (N=629)		
Number of elevated IOP events (n)	67	125		
Maximum IOP (mmHg)	n (%)	n (%)		
< 30	17 (5.2)	40 (6.4)		
≥ 30	50 (15.3)	85 (13.5)		
$\geq$ 40	23 (7.0)	38 (6.0)		
$\geq$ 50	13 (4.0)	24 (3.8)		
$\geq 60$	6 (1.8)	11 (1.7)		
$\geq 70$	0 (0.0)	1 (0.2)		

Table 3:	Maximum	IOP	Among	Incidences	of	Elevated	IOP	with	Onset	at
Postopera	tive Visit 0 (	Safety	y Populat	tion)						

Source: Table 13, EVO/EVO+ DFU

Percentage calculated as (n/N)\*100.

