## **Statistical Analysis**

Summaries for continuous variables will include the number of non-missing values, mean, standard deviation, median, minimum, and maximum. Summaries for discrete variables will include the tabulation of frequencies and percentages. Analyses of increases in IOP attributed to other causes will include distribution of maximum IOP measured and summaries of causes and treatments used. A presentation of all relevant clinical observations and symptoms, severity, diagnoses, treatments, duration, resolution, and sequelae will be provided for all significant AEs. In addition, classification of whether each event was a "serious adverse event" or "device or procedure-related" will be provided. Rates and descriptions of all device deficiencies and SAEs observed during the course of the study will be provided.

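### The benchmarks of 15.3% and 7.0% are tabulated by the maximum IOP of events with onset at Visit 0, the endpoints are IOP at 1–6 hours, and no planned analysis applies one rule to both

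*Combined protocol and SAP*

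**What the plan says.** **Endpoints.** Section 7.2 counts "the proportion of primary eyes that have IOP ≥ 30 mmHg" at 1–6 hours after surgery, and separately those at 40 mmHg or more. The data come from Visit 1, where under section 5.1.3.1 "an IOP reading and slit lamp examination in the implanted eye(s) will be conducted".

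**Benchmarks.** Section 7.0 compares these proportions with 15.3% (50/327) and 7.0% (23/327) from Study CP19-01, citing Table 3 of that section. The table opens with "Number of elevated IOP events (n", 67 in primary eyes, and sorts them under "Maximum IOP (mmHg": 17 below 30, 50 at 30 or more, 23 at 40 or more. Its title restricts the events to those that began at Visit 0. It does not say over what period the maximum was taken.

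**Later readings.** In this study IOP is measured again on Day 1, Days 5–9 and Days 10–18. Section 5.1.4 says: "An IOP reading will be performed at these visits in addition to other standard postoperative assessments".

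**Planned use of maximum IOP.** Under Statistical Analysis in section 7.2: "Analyses of increases in IOP attributed to other causes will include distribution of maximum IOP measured". This does not cover rises from retained viscoelastic, the mechanism that the training targets (section 1.0). The rates of increased IOP planned over the whole follow-up carry no 30 or 40 mmHg threshold and no comparison with CP19-01.

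**The concern.** In a single-arm study the fixed rate is the only control, so both sides of the comparison should be measured in the same way. As written they are not. Take an eye at 28 mmHg at Visit 1, recorded as an elevated-IOP event, that reaches 42 mmHg on Day 1. Under the heading of Table 3 it belongs in the ≥40 row. Under section 7.2 it counts for neither endpoint.

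Two effects pull in opposite directions:

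- **Maximum against single reading.** For the tabulated events, a maximum is at least as high as the onset reading. Counted by the Visit 0 reading, those events number 50 and 23 or fewer. This would make the benchmark too high and the test too easy to pass.
- **Adverse events against all eyes.** Table 3 counts only recorded adverse events; the endpoint counts any eye over the threshold. Under this protocol's own rule (section 6.1.1), an untreated 30 mmHg reading from a baseline of 21 mmHg is a rise of 9 mmHg and need not be reported in the first week. If CP19-01 used a similar rule (not stated), some readings of 30 or more could be missing from the table, making the benchmark too low.

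What is at stake is whether a pass shows fewer early pressure rises or partly reflects a change in how they are counted.

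**Working it through.** **Inputs**

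- Exact one-sample binomial test, two-tailed alpha 0.05, so 0.025 in the lower tail (section 7.3).
- Benchmarks 50/327 = 15.29% and 23/327 = 7.03% (section 7.0). Row check: 17 + 50 = 67 events.
- Planned rates 6% and 1% (section 7.1); 181 evaluable eyes and 200 enrolled (section 7.3).
- k = number of benchmark eyes that reached the threshold only after their Visit 0 reading. The documents give no value. Every k below is an assumption, and zero is possible.

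**Step 1: the plan's own power.** The pass limit c is the largest count with P(X ≤ c | n, p0) ≤ 0.025; power is P(X ≤ c | n, p1). At n = 181:

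- ≥30 mmHg: c = 18, tail 0.0244, power 98.7%. The plan states 98%, which reproduces.
- ≥40 mmHg: c = 5, tail 0.0106, power 99.0%. The plan states 96%, which is P(X ≤ 4) = 96.4%, a limit one eye stricter than needed. The difference is conservative and does not affect this point.

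**Step 2: pass limits at n = 200**

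- ≥30 mmHg: P(X ≤ 20 | 50/327) = 0.0196 and P(X ≤ 21) = 0.0326, so the limit is 20 eyes.
- ≥40 mmHg: P(X ≤ 6 | 23/327) = 0.0114 and P(X ≤ 7) = 0.0264, so the limit is 6 eyes.

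**Step 3: chance of a false pass.** Suppose training changes nothing and the like-for-like 1–6 hour rates are (50 − k)/327 and (23 − k)/327. Keep the limits of 20 and 6.

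| k | ≥30 rate | P(X ≤ 20) | ≥40 rate | P(X ≤ 6) |
|---|---|---|---|---|
| 0 | 15.3% | 2.0% | 7.0% | 1.1% |
| 3 | 14.4% | 4.3% | 6.1% | 3.6% |
| 5 | 13.8% | 7.0% | 5.5% | 7.3% |

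**Step 4: passing both.** Eyes at ≥40 are a subset of eyes at ≥30, so

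P(both) = Σ over x ≤ 20 of Bin(x; 200, p30) × P(Y ≤ 6 | x, p40/p30).

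- k = 0 and 0: 0.3%
- k = 5 and 5: 2.4%
- k = 10 and 5: 4.7%

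**Step 5: cost of a lower benchmark.** At true rates of 6% and 1%, the same formula gives the power to pass both:

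- limits 20 and 6: 98.7%
- limits 19 and 5: 96.8%
- limits 17 and 4 (the limits at k = 5 and 5): 90.3%

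**The case against.** **No late-peaking eye is shown.** Table 3 is taken from the Directions for Use, which are not among the documents. Onset at Visit 0 is compatible with every maximum being the Visit 0 reading, and then the only remaining gap is the restriction to adverse events. This stands: what is established is an undefined benchmark measure, not a wrong figure. A reader might infer that 15.3% and 7.0% are inflated and that a pass would be spurious. The documents do not support that, because neither the size nor the net direction of any error can be read from them.

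**One eye does not make the test fragile.** A reader who recomputes the limits will see that a single late eye (49/327) lowers the ≥30 limit from 20 to 19 and might call the result sensitive to one eye. That is mostly the discreteness of the exact test: the tail moves from 0.0196 to 0.0258, just past 0.025. The ≥40 limit needs three late eyes to move. With both endpoints required, the chance of a false pass is still 2.4% with 5 assumed late eyes at each threshold.

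**The power cost may be overstated.** The planned 6% is "Based on Study CP19-01 data from investigators who followed the instructions" on viscoelastic removal (15/240 in Table 4 of section 7.1). If that table used the same maximum, which is not stated, the planned rate would fall along with the benchmark. Scaling only the 6%, to 6% × 49/50 = 5.88%, gives 97.1% rather than 96.8% with limits 19 and 5. This is fair but small.

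**Late rises are partly captured.** A rise of at least 10 mmHg above baseline to 25 mmHg or more, or any treated rise, is an adverse event whenever it occurs (section 6.1.1), and rates by cause are reported through Visit 4. The data will therefore exist. What is missing is a comparison by the 30 and 40 mmHg thresholds with the benchmark.

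**Conclusion.** The mismatch is in the text and is worth closing because it is cheap to close, not because it has been shown to distort the result. The benchmark is defined by an event's maximum, the endpoint by the 1–6 hour pressure, and nothing planned reconciles them. The net bias is unknown, probably small and possibly zero. Five late-peaking eyes at each threshold would raise the chance of a false pass from 2.0% to 7.0% and from 1.1% to 7.3% per endpoint, and from 0.3% to 2.4% for both. If training works as assumed, the study would probably pass on either definition.

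These figures assume 200 evaluable primary eyes, one event per eye in Table 3, no offsetting readings missed by the adverse-event count, and values of k chosen only to show scale.

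**What to change.** Keep the 1–6 hour primary and secondary endpoints, and add to section 7.2:

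1. State when CP19-01's Visit 0 took place and over what period its maximum IOP was taken. Retabulate all CP19-01 primary eyes by the IOP reading at that visit (1–6 hours), whether or not it was recorded as an adverse event. Show the counts beside 50/327 and 23/327. If they differ in either direction, run the exact test against the retabulated rates as a prespecified sensitivity analysis.
2. Prespecify a supportive analysis that classifies this study's primary eyes by the maximum IOP of elevated-IOP events with onset at Visit 1, over the same period as the CP19-01 maximum as far as the visits allow, and compare it with 15.3% and 7.0%.

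The cost is a few sentences and one retabulation of data that the sponsor already breaks down by site in Table 4. No visits, measurements or treatments change. The downside is that a lower like-for-like benchmark is slightly harder to beat: the power to pass both endpoints is 96.8% instead of 98.7% at 6% and 1% if each limit drops by one eye. If the retabulation returns 50 and 23, the question is closed.

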## **Statistical Analysis**

Summaries for continuous variables will include the number of non-missing values, mean, standard deviation, median, minimum, and maximum. Summaries for discrete variables will include the tabulation of frequencies and percentages. Analyses of increases in IOP attributed to other causes will include distribution of maximum IOP measured and summaries of causes and treatments used. A presentation of all relevant clinical observations and symptoms, severity, diagnoses, treatments, duration, resolution, and sequelae will be provided for all significant AEs. In addition, classification of whether each event was a "serious adverse event" or "device or procedure-related" will be provided. Rates and descriptions of all device deficiencies and SAEs observed during the course of the study will be provided.

## 7.3 Sample Size

For a single sample exact binomial test with a two-tailed alpha of 0.05 to demonstrate that a hypothesized rate of 6% is significantly lower than 15.3% for IOP spikes  $\geq$  30 mmHg with 98% power, a sample of 181 eyes would be required. Demonstrating that the rate of IOP spikes  $\geq$  40 mmHg is significantly lower, given a hypothesized rate of 1% vs the Study CP19-01 rate of 7%, a sample size of 181 primary eyes of 181 subjects will achieve 96% power. Power to achieve both endpoints can be conservatively estimated by

the product of the two powers, .98 times .96, or 94%. Analysis of fellow eye rates will also be conducted, and results will be used to support the findings of the two primary eye analyses. We assume no more than 10% loss to follow up in this 2-week study, so plan to enroll a minimum of 200 subjects (i.e., 200 primary eyes and 200 fellow eyes).

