## SYNOPSIS

STAAR Surgical Company Study #CP22-01: Post-Market Evaluation of the EVO ICL				
Revision chronology:	Rev 1, 06May2022			
Title:	Post-Market Evaluation of the EVO ICL			
Type of study:	Post-approval study (PAS)			
Objective(s):	To assess the rate of early intraocular pressure (IOP) increases following implantation of EVO/EVO+ICL lenses (EVO ICL).			
Study design:	This new enrollment, prospective, multi-center, single arm PAS will be conducted at up to 10 clinical sites in the United States (US). The study is designed to evaluate the success of the EVO Physician Certification Program in reducing the rate of early IOP increases at 1 – 6 hours after implantation of EVO ICL lenses by surgeons who have been trained and certified under the EVO Physician Certification Program.			
	This PAS will enroll a minimum of 200 subjects (i.e., 200 primary eyes and 200 fellow eyes) who are eligible for EVO ICL surgery in both eyes. All subjects are intended to undergo bilateral implantation with the second-eye surgery occurring from $1 - 14$ days ( $1 \le 14$ days) following the day of first eye surgery. Surgeons will use 2% HPMC OVD for EVO ICL surgery as recommended in the EVO ICL Directions for Use (DFU).			
	Subjects will be seen for 4 postoperative visits at the following timepoints:			
	
 
1 - 6 hours postoperatively
 
1 day postoperatively
 
5 - 9 days postoperatively
 
10 - 18 days postoperatively
 
			
Study duration:	This study is expected to require approximately 28 months following initiation, including approximately 24 months for enrollment, approximately $2-3$ weeks for follow-up of each eye and approximately 3 months for data analysis and reporting.			
Eligibility criteria:	Subjects aged 21 to 45 years implanted with EVO ICLs in both eyes, in accordance with the product labeling and the following eligibility criteria:			
	Inclusion Criteria			
	1. Subjects 21 through 45 years old at time of surgery.			
	2. For EVO ICL for Myopia:			
	• Moderate to high myopia ranging from -3.00 D to $\leq$ -20.00 D spherical equivalent (SE) in the spectacle plane with less than or equal to 2.50 D of astigmatism (in the spectacle plane).			
	For EVO Toric ICL for Myopia with Astigmatism:			

Г

STAAR Surgical	Company Study #CP22-01: Post-Market Evaluation of the EVO ICL

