#### (EVO/EVO+ Toric Lenses)

The EVO TICL is indicated for use in patients 21-45 years of age:

- for the correction of myopic astigmatism with spherical equivalent ranging from -3.0 D to ≤ -15.0 D (in the spectacle plane) with cylinder (spectacle plane) of 1.0 D to 4.0 D;
- 2. for the reduction of myopic astigmatism with spherical equivalent ranging from greater than -15.0 D to -20.0 D (in the spectacle plane) with cylinder (spectacle plane) 1.0 D to 4.0 D;
- 3. with an anterior chamber depth (ACD) of 3.00 mm or greater, when measured from the corneal endothelium to the anterior surface of the crystalline lens and a stable refractive history (within 0.5 D for both spherical equivalent and cylinder for 1 year prior to implantation).
- 4. The EVO TICL lens is intended for placement in the posterior chamber (ciliary sulcus) of the phakic eye.

All surgeons are required to be certified by STAAR Surgical Company (STAAR) prior to being granted access to order STAAR ICLs for their patients. The EVO Physician Certification Program has been revised to align with the device labeling approved by the FDA. STAAR is conducting a Post-Approval Study (PAS) designed to evaluate the

effectiveness of the EVO certification training program in reducing the risks of early postoperative Intraocular Pressure (IOP) increases due to incomplete removal of 2% hydroxypropylmethylcellulose (HPMC) ophthalmic viscoelastic device (OVD).

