## 3.3 Investigators

The study will be conducted at up to 10 clinical site(s) located in the US.

The study will be conducted by Investigator surgeons who have been trained and certified under the STAAR EVO Certification Program and who have been determined to be suitably qualified by training and experience to conduct this study in compliance with all applicable Good Clinical Practices (GCPs) and FDA Federal Regulations.

Sub-Investigators will be identified on the Device Investigator Agreement (DIA)/ Delegation of Authority Log (DOA).

Each Investigator will enroll approximately 20 subjects (40 eyes) and no individual site may enroll more than 25% of the total enrollment.

In the event that selected sites do not meet full enrollment, the Sponsor may decide to increase enrollment as needed at other currently active sites and additional site(s) may be added to satisfy the enrollment requirements of the study.

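### Does the exact binomial test need by-site rates or a site-clustered interval because the study evaluates surgeon training?

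*Combined protocol and SAP*

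**What the plan says.** The Synopsis gives the purpose: "The study is designed to evaluate the success of the EVO Physician Certification Program in reducing the rate of early IOP increases". The Introduction likewise speaks of the "effectiveness of the EVO certification training program in reducing the risks of early" IOP increases. Section 2.0 states the objective more narrowly, as assessing the rate of early IOP increases after implantation. Section 7.2 defines the primary endpoints as two proportions of primary eyes, at ≥ 30 and ≥ 40 mmHg, 1 to 6 hours after surgery.

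The test appears in section 7.3: "For a single sample exact binomial test with a two-tailed alpha of 0.05". For the pair of endpoints, "Power to achieve both endpoints can be conservatively estimated by" multiplying the two powers, 0.98 and 0.96, to give 94%. On descriptive output, section 7.2 says: "Summaries for discrete variables will include the tabulation of frequencies and percentages". It names no breakdown by site, and it rules none out.

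Site enters through the enrolment rules of section 3.3: "Each Investigator will enroll approximately 20 subjects (40 eyes) and no individual site may enroll more than 25% of the total enrollment". The same section allows more than one surgeon at a site: "Sub-Investigators will be identified on the Device Investigator Agreement". By-site planning data stand in Table 4 of section 7.1, captioned "Incidence of elevated IOP in primary eyes for investigators who followed" the proposed instructions for removing the viscoelastic.

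**The concern.** Training acts through the surgeon, so eyes treated at one site may share a risk. If they do, and if the conclusion is meant for certified surgeons in general, a test that treats eyes as independent has too narrow an interval and too high a false-positive rate. Table 4 appears to show such variation: among primary eyes the ≥ 30 mmHg rate runs from 0% to 15.8% (3/19). A pass close to the limit could then depend on which sites enrolled most eyes, and the plan specifies no table or interval to show it. At stake would be the claim that the programme lowered the early IOP rates.

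**Working it through.** **1. The plan's own figures.** Inputs from section 7.3: n = 181, benchmark rates 15.3% and 7.0%, planned rates 6% and 1%, 0.025 in the lower tail. The pass limit c is the largest count with P(X ≤ c | benchmark) ≤ 0.025; power is P(X ≤ c | planned rate).

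| Endpoint | Limit, n = 181 | Lower-tail error | Power | Stated power | Limit, n = 200 |
|---|---|---|---|---|---|
| ≥ 30 mmHg | 18 | 2.42% | 98.7% | 98% | 20 |
| ≥ 40 mmHg | 5 | 1.11% | 99.0% | 96% | 6 |

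The 98% reproduces. The 96% matches a limit of 4/181 (96.4%), so it errs on the cautious side. The product 0.98 × 0.96 = 0.94 is right.

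**2. How much site variation Table 4 supports.** Primary eyes ≥ 30 mmHg by site: 5/39, 3/19, 1/10, 1/11, 0/29, 1/76, 0/12, 0/8, 4/31, 0/5, in total 15/240. With the one-way ANOVA estimator, ICC = (MSB − MSW) / [MSB + (n₀ − 1) MSW], where MSB = 0.0997, MSW = 0.0572 and n₀ = 22.08:

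ICC = 0.0425 / (0.0997 + 21.08 × 0.0572) = 0.0325.

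The heterogeneity chi-square is 15.3 on 9 df, p = 0.083. Without the 1/76 site the ICC is −0.0002 (p = 0.43). That site held 76/240 = 31.7% of the eyes, above the 25% cap of section 3.3. For ≥ 40 mmHg there were 0/240 events, so no ICC can be estimated.

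**3. What that ICC would do to a result.** Take 10 sites of 20 eyes. Design effect = 1 + (20 − 1) × 0.0325 = 1.62; effective n = 200/1.6175 = 123.6. Upper Clopper-Pearson limits (two-sided 95%), clustered by dividing events and eyes by the design effect:

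| Result | Unclustered | Clustered | Benchmark |
|---|---|---|---|
| 12/200, planned rate ≥ 30 | 10.2% | 11.7% | 15.3% |
| 20/200, pass limit ≥ 30 | 15.0% | 16.7% | 15.3% |
| 2/200, planned rate ≥ 40 | 3.6% | 4.7% | 7.0% |
| 6/200, pass limit ≥ 40 | 6.4% | 7.7% | 7.0% |

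The largest counts that clear the benchmark fall from 20 to 17 and from 6 to 4. The two readings differ only at 18 to 20 (≥ 30 mmHg) and 5 to 6 (≥ 40 mmHg). At the planned rates the chance of landing there is about 5% (ICC 0) to 7% (ICC 0.0325) for each endpoint.

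**4. Error and power of the planned test under clustering.** Simulation with nested outcomes (≥ 40, 30 to 39, < 30 mmHg) and Dirichlet site effects. Designs: 10 × 20 eyes, 181 eyes at equal sites, and 181 eyes at assumed uneven sites (45 down to 5 eyes).

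- ≥ 30 mmHg alone, true rate at benchmark, 10 × 20: error 1.9% at ICC 0, 5.2% at 0.0325, 7.0% at 0.05.
- Both endpoints required, both true rates at benchmark: 0.3% at ICC 0, 1.2% to 1.7% at 0.0325, 1.8% to 2.6% at 0.05.
- Joint power at the planned rates, ICC 0.0325: 94.9% (10 × 20), 93.5% (181, equal), 91.4% (181, uneven).

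**The case for a change.** The strongest counter-argument uses the protocol's own planning data. If the 240 eyes in Table 4 are a subset of the 327 primary eyes in section 7.0, with the same event definition, the other 327 − 240 = 87 eyes had 50 − 15 = 35 events ≥ 30 mmHg (40%) and all 23 events ≥ 40 mmHg (26%). Site practice would then have driven the earlier result. Uneven sites also raise the effect: a robust design effect computed on Table 4 is about 2.6, at which 11/181 still clears its benchmark but 2/181 would not (it fails from 2.51). The single-endpoint error does exceed 2.5% if site variation is real. If the true ≥ 30 mmHg rate were 8% to 10%, the chance of a count of 18 to 20 would be 18% to 27%.

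Part of this stands: by-site rates would be informative, and the plan does not specify them. It does not amount to a fault in the planned test. The 87-eye contrast, itself an assumption, separates investigators who followed the instructions from the rest, whereas here every surgeon must be certified; a site that still performed badly would add events and work against a pass. The 2.6 comes from a layout with 31.7% of eyes at one site and is borrowed for an endpoint with no events. When both endpoints must pass, an error of 5% to 7% at ICC 0.0325 needs ≥ 40 mmHg to fall to 1% while ≥ 30 mmHg does not improve at all.

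Nor is a clustered interval clearly better. With the design effect estimated from about 10 sites at ICC 0.0325, its upper limit falls below the ≥ 30 mmHg benchmark in 3.0% to 4.1% of runs when the true rate is at that benchmark. At the planned rates it contradicts a passing exact test in 11% to 14% (≥ 30) and 8% to 9% (≥ 40) of runs, and for ≥ 40 mmHg it makes no adjustment in 41% to 53%.

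**Conclusion.** The concern does not hold. The plan specifies no by-site or clustered analysis, but no stated number, rule or property of the test is thereby wrong. Section 2.0 and section 7.2 frame the question as rates among eyes, and for the enrolled sites taken as fixed the exact binomial interval is adequate. The Synopsis and Introduction can be read as aiming at certified surgeons in general. Under that reading results at the planned rates still pass at ICC 0.0325, joint error with both rates at benchmark stays at or below about 2.6% up to ICC 0.05, and joint power at 0.0325 is 91.4% to 94.9% against the stated 94%. What remains is a narrow band of counts below the pass limit, and its width rests on an ICC that vanishes when one site is removed.

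This rests on four assumptions: success requires both endpoints, as the joint power in section 7.3 implies; the ICC lies between 0 and 0.05 and is the same for both endpoints; an ICC seen at a rate near 6% carries over to 15.3% and 7.0%; and site stands in for surgeon. A by-site table would be reasonable extra description, and leaving it unspecified is a choice open to the sponsor.

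### Section 7.3 understates its power: the exact test it names gives 99.0% for IOP ≥40 mmHg, not 96%, and 97.7% jointly, not 94%

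*Combined protocol and SAP*

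**What the plan says.** Section 7.0 sets the two primary-eye rates against fixed reference rates from Study CP19-01: 15.3% (50/327) for ≥30 mmHg and 7.0% (23/327) for ≥40 mmHg. Section 7.1 assumes true rates of 6% and 1%.

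Section 7.3 names the test and its level: "For a single sample exact binomial test with a two-tailed alpha of 0.05". It gives 98% power for ≥30 mmHg with 181 eyes. For ≥40 mmHg, "given a hypothesized rate of 1% vs the Study CP19-01 rate of 7" percent, it says that "a sample size of 181 primary eyes of 181 subjects will achieve 96% power". The power to meet both endpoints is then taken, as a conservative estimate, to be "the product of the two powers, .98 times .96, or 94" percent. Finally, "We assume no more than 10% loss to follow up in this 2-week study", which leads to the enrolment target of 200 subjects.

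No other test, alpha or sample size is given for the ≥40 mmHg figure. Section 7.2 lists the endpoints and summaries but states no test or rejection limit.

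**The concern.** Section 7.3 supplies everything needed to recompute its powers: test, alpha, sidedness, n, and null and alternative rates. The ≥40 mmHg power does not come out at 96%, and the joint figure inherits the discrepancy.

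The design itself is not at risk, because the true power is higher than the one printed. What is at stake is whether the paragraph can be reproduced, and whether the success criterion is clear. Section 7.3 is the only place where the test and its level appear. A reader who works back from 96% would infer that success on ≥40 mmHg means at most 4 of 181 eyes, whereas the stated test succeeds at 5. Both are primary endpoints judged against fixed rates, so that boundary should not be ambiguous.

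**Working it through.** **Inputs.** n = 181; two-tailed alpha 0.05; ≥30 mmHg p0 = 0.153, p1 = 0.06; ≥40 mmHg p0 = 0.07, p1 = 0.01 (all Section 7.3). Unrounded reference rates are 50/327 and 23/327 (Section 7.0).

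**Formula.** With X the number of eyes at or above the threshold, the rejection limit c is the largest integer with P(X ≤ c | 181, p0) ≤ 0.025. Power is P(X ≤ c | 181, p1).

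**The plan's own multiplication.** 0.98 × 0.96 = 0.941, printed as 94%. The multiplication is right; the question is what goes into it.

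**≥30 mmHg**

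| Limit c | P(X ≤ c) at 15.3% | Power at 6% |
|---|---|---|
| 16 | 0.0073 | 0.9544 |
| 17 | 0.0137 | 0.9750 |
| **18** | **0.0242** | **0.9870** |
| 19 | 0.0405 | 0.9936 |

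The limit is 18 and the power 98.7%. The printed 98% is reproduced to within rounding down.

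**≥40 mmHg**

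| Limit c | P(X ≤ c) at 7% | Power at 1% |
|---|---|---|
| 3 | 0.0010 | 0.8907 |
| 4 | 0.0038 | 0.9637 |
| **5** | **0.0111** | **0.9898** |
| 6 | 0.0272 | 0.9975 |

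The limit is 5 and the power 99.0%. The printed 96% is not reproduced.

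**Product.** 0.9870 × 0.9898 = 0.977, against 94% printed.

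**Could another reasonable reading give 96%?**

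- *Two-sided convention.* At 18 eyes the two-sided p-value is 0.0484 (doubled tail) or 0.0491 (minimum likelihood). At 5 eyes it is 0.0221 or 0.0194, and at 6 eyes 0.0544 or 0.0564. The limits are 18 and 5 under both conventions.
- *Unrounded reference rates.* With 50/327 and 23/327 the limits are again 18 and 5, so the powers do not change.
- *Neighbouring n.* The ≥40 mmHg power is 0.9900 at n = 180 and 0.9895 at n = 182.
- *Approximations at n = 181.* Normal 0.9990, continuity-corrected normal 0.9967, arcsine 0.9946. With only the null variance, the normal approximation gives 0.886. A two-sample comparison with the 327 eyes gives 0.906 (pooled) or 0.923 (Fisher). None is 0.96.
- *A stricter common alpha.* Only a limit of 4 gives 96% (96.4%). For 5 eyes not to reject, the two-tailed alpha must be below about 0.022 (doubled tail) or 0.0194 (minimum likelihood). At such an alpha the ≥30 mmHg limit is at most 16 and its power at most 95.4%, not 98%. With rates of exactly 6% and 1%, the two printed powers therefore cannot come from one exact test at a common alpha.

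**A possible source (inference only).** Limits one eye too strict, 17 and 4, give 0.9750 and 0.9637, with product 0.940. Rounded, these match all three printed figures, as they would if a strict inequality had been used where the limit itself should count. The documents do not say so.

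**At the planned attrition.** 200 × 0.9 = 180 eyes. Doubled tail: limits 17 and 5, powers 0.9762 and 0.9900, product 0.9665. Minimum likelihood: limits 18 and 5, powers 0.9877 and 0.9900, product 0.978. Both products exceed 94%.

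**The case against.** The best case for the printed figures is that the assumed rates are themselves rounded. The 6% rests on 15/240 = 6.25% in Table 4 of Section 7.1. At that rate and a limit of 18, power is 98.1%, which prints as 98%. In the same way, a rate a little above 1% could lie behind the 96%: with a limit of 5, power is 96.8% at 1.3% and 95.7% at 1.4%. On that reading both printed powers come from one test at alpha 0.05.

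This stands as a qualification: the claim that one alpha cannot yield both powers holds only for the rates as printed. It does not rescue the 96%. The documents give no decimal for the 1%, Table 4 shows 0/240 at ≥40 mmHg, and Section 7.3 states 1%.

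Three narrower points are fair. The 98% for ≥30 mmHg can be read as a level that 181 eyes must reach, and they do reach it, so it is not an error in itself. The 94% is a consequence of the 96%, not a second mistake. And no design criterion depends on either figure, since the plan sets no minimum power for ≥40 mmHg or for the joint result. These points limit the weight of the finding but leave the arithmetic as it is.

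**Conclusion.** The concern holds. For the test, alpha, rates and n printed in Section 7.3, the ≥40 mmHg power is 99.0% rather than 96%, an understatement of 3.0 points. The joint power by the plan's own rule is 97.7% rather than 94%, an understatement of about 4 points. The ≥30 mmHg figure is sound apart from rounding (98.7% against 98%).

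The result assumes that 6% and 1% are exact and, for the joint figure, accepts the plan's product rule. It does not depend on the two-sided convention or on rounding of the reference rates. Because the error is conservative, 181 evaluable eyes and 200 enrolled subjects remain adequate. This is a definite numerical error of low consequence that should be corrected.

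**What to change.** Restate the three figures in Section 7.3 together: 98.7% for ≥30 mmHg, 99.0% for ≥40 mmHg, and a product of 97.7% (about 98%). Changing only 96% to 99% would leave 0.98 × 0.99 = 97.0%, still short of the product of the unrounded powers. Add the rejection limits at 181 eyes, at most 18 for ≥30 mmHg and at most 5 for ≥40 mmHg, and name the two-sided convention. The convention matters if 180 eyes are analysed, where the ≥30 mmHg limit is 17 (doubled tail) or 18 (minimum likelihood).

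If an unrounded rate, another alpha or another limit was intended for either endpoint, state it instead and show that it gives the printed power.

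The cost is three figures and one added sentence in a single paragraph. Sample size, enrolment and analysis do not change.
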